### **7.7. Storage and Analysis of Samples**

Routine blood/laboratory tests will be analysed in a local NHS laboratory at the Royal Derby Hospital, which is serviced and managed according to national standards and governance frameworks. Following analysis, samples will be destroyed according to local practice and no samples will be kept for longer than required for the study.

### **7.8. End of Study**

The end of study will be defined as when the final patient attends for their last assessment. The CI will notify the Sponsor and REC within 90 days of the end of study. The clinical study report will be written within 12 months of the end of study.

## **8. SAFETY REPORTING**

### **8.1. Definitions**

Term	Definition
Adverse Event (AE)	Any untoward medical occurrence in a participant, including occurrences which are not necessarily caused by or related to study procedures.
Related AE	An untoward and unintended response in a participant to a study procedure. This means that a causal relationship between the study procedure and an AE is at least a reasonable possibility, i.e. the relationship cannot be ruled out.
Serious Adverse Event (SAE)	A serious adverse event is any untoward medical occurrence that: 

• results in death

• is life-threatening

• requires inpatient hospitalisation or prolongation of existing hospitalisation

• results in persistent or significant disability/incapacity

• consists of a congenital anomaly or birth defect

 Other 'important medical events' may also be considered serious if they jeopardise the participant or require an intervention to prevent one of the above consequences. NOTE: The term "life-threatening" in the definition of "serious" refers to an event in which the participant was at risk of death at the time of the event; it does not refer to an event which hypothetically might have caused death if it were more severe.
Related SAE	An adverse event that is both serious and, in the opinion of the reporting Investigator, believed with reasonable probability to be due to one of the study procedures.

Related & Unexpected SAE	A serious adverse event that: 
 
• is believed with reasonable probability to be due to one of the study procedures.
 
• the nature and severity of which is not consistent with the information provided in the protocol i.e. it is not listed as an expected occurrence.
 

-------------------------------------	--

## 8.2. Operational Definitions for (S)AEs

As a low-risk intervention, there is no requirement for non-serious AEs to be recorded or reported. Any AEs that meet the definition of serious (SAE) as per Section 8.1 and are not listed below must be reported.

Exceptions to SAE reporting:

- *Rejection*
- *Infection*
- *Graft Failure*
- *New Onset Diabetes after Transplantation*

The following circumstances are usually not considered SAEs:

- Routine treatment or monitoring of the studied indication not associated with any deterioration in condition.
- Treatment, which was elective or pre-planned, for a pre-existing condition not associated with any deterioration in condition.
- Any admission to hospital or other institution for general care where there was no deterioration in condition.
- Treatment on an emergency, outpatient basis for an event **not** fulfilling any of the definitions of serious as given above and not resulting in hospital admission.

In all cases AEs and/or laboratory abnormalities that are critical to the safety evaluation of the participant must be reported. Where certain AEs are not required to be reported to the Sponsor (e.g. expected SAEs for the disease or intervention), these should be listed in the protocol and still be recorded in the participant's medical records.

## 8.3. Recording and Reporting SAEs

All AEs and SAEs must be recorded from the time of written informed consent until after the last visit. All (S)AEs occurring during the duration of the study must be reported by the investigator within the CRF. The PI is responsible for checking for AEs when participants attend for treatment and follow-up. All related and unexpected SAEs must be recorded by the investigator using the 'non-CTIMP safety report to REC form' from the HRA website. The completed form should be submitted to the Sponsor and REC within 15 days of the CI becoming aware of the event. Safety information will be reviewed during trial management group meetings.

### **8.3.1. Assessment of AEs and SAEs**

#### **8.3.1.1 Severity**

The investigator should determine the severity of the AE:

- Mild: no interference with daily activities.
- Moderate: moderate interference with daily activities.
- Severe: considerable interference with daily activities (e.g. inability to work).

**NOTE:** to avoid confusion or misunderstanding, the term “severe” is used to describe the intensity of the event, which may be of relatively minor medical significance, and is NOT the same as “serious” which is described in the safety definitions.

#### **8.3.1.2 Causality**

Clinical judgement should be used to determine the relationship between the study procedures and the occurrence of each AE:

- Not-related: There is no evidence of a causal relationship between the event and study procedures.
- Related: There is evidence of a causal relationship between the event and study procedures i.e. a relationship to the study procedures cannot be completely ruled out.

Assessment of causality must be made by a medically qualified doctor (usually the PI).

#### **8.3.1.3 Expectedness**

The assessment of expectedness is only required if the event is deemed to be related to study procedures.

- Expected: Event previously identified and described in the protocol.
- Unexpected: Event not previously described in the protocol.

The expectedness assessment is delegated to [name].

### **8.4. Pregnancy reporting**

If a participant becomes pregnant or is suspected to be pregnant from the time of consent up to the final study visit, they will be withdrawn from the study. There is no follow-up reporting required.

## **8.5. Reporting Urgent Safety Measures**

If any urgent safety measure is taken, the research team should inform the Sponsor with 24 hours using the Sponsors safety incident reporting form. The Sponsor will inform the REC and participating sites of the measures taken and the circumstances giving rise to those measures within 3 days on implementation of the urgent safety measure.

## **9. DATA HANDLING**

### **9.1. Data Collection Tools and Source Document Identification**

Data will be collected on a CRF (paper) and transcribed onto an electronic database. CRFs will be stored as part of the ISF, which will be kept in a secure location with restricted access.

### **9.2. Source Data**

For the purposes of this study, source data shall be defined as medical records of the participant (electronic or paper), any self-reported questionnaires and in some instances, the CRF may serve as its own source data for information collected directly from the participant.

### **9.3. Data Handling and Record Keeping**

A validated spreadsheet (the database) will be developed and used for the transcription of data from the CRF, as described in the applicable SOP of the Sponsor. Validation will ensure data is entered in the correct format at the point of transcription in an effort to reduce transcription errors. The database will be stored on an NHS computer on a drive that is regularly backed up to a centrally hosted server (in the UK). Access to the database will be password protected and limited only to the appropriate members of the research team.

All data collected on the CRF and subsequently on the database will be pseudonymised, containing no identifiable data and using only a unique study ID to identify the study participant.

### **9.4. Access to Data**

Direct access will be granted to authorised representatives from the Sponsor, host institution and the regulatory authorities to permit study-related monitoring, audits and inspections.

### **9.5. Archiving**

At the end of the study, following completion of the end of study report, UHDB will securely archive all centrally held study related documentation for a minimum of 5 years. At the end of the defined archive period, arrangements for confidential destruction will be made. It is the responsibility of the Investigator to ensure that data and all essential documents relating to the study are retained securely for a minimum of 5 years after the end of study, and in accordance with national legislation. UHDB will notify the Investigator when study documentation may be archived, and then destroyed.

All archived documents must continue to be available for inspection by appropriate authorities upon request.

## **10. STATISTICS AND DATA ANALYSIS**

Statistical analysis will be undertaken by [name] [name] with support from [name] and [name]. Data management and statistical analyses will be performed using statistical software SPSS version 26.0.

To compare baseline versus final evaluations, Wilcoxon test or paired t-test will be used in the case of dimensional variables, and McNemar test in the case of categorical variables. Intergroup comparisons will be performed using Mann Whitney test or Student t test for continuous variables and  $\chi^2$  test or Fisher's exact test for categorical variables.

### **10.1. Sample Size Calculation**

As this is a feasibility RCT, no formal sample size calculation is required; however, the aim will be to recruit 40 kidney transplant recipients to test the study procedures and the feasibility of delivering the intervention. Power calculation using ClinCalc indicates that, assuming an SAF value of  $2.81 \pm 0.64$  AU in the control group (Crowley et al., 2013), having a sample size of 18 in each group would give 80% power ( $\alpha=0.05$ ) to detect a difference in SAF of 0.6 AU between the groups at 6 months. The proposed recruitment would achieve this and allow for 10% drop-out.

### **10.2. Planned Recruitment Rate**

This is a single centre pilot study aiming to recruit 40 adult (>18 years) kidney transplant recipients. This centre's kidney transplant recipient population numbers more than 300. With around 50 kidney transplant recipients attending for outpatient follow-up weekly, it is expected that the recruitment duration will be minimal.

### **10.3. Statistical Analysis**

#### **10.3.1. Summary of Baseline Data and Flow of Patients**

Descriptive statistics will be presented to summarize the distribution of baseline variables across each of the randomisation groups. The continuous baseline variables (e.g. SAF, age, height, weight and blood pressure) will be reported with means and standard deviations, if shown to be normally distributed, using a combined skewness and kurtosis test, otherwise will be reported with medians and Interquartile Ranges (IQR). The categorical variables (e.g. sex, ethnicity and employment status) will be reported with frequencies and percentages.

A Consolidated Standards of Reporting Trials (CONSORT) flow diagram will be produced, showing the frequency of patients/participants:

- Assessed for eligibility or found eligible,
- Excluded before randomisation (and the frequency of each reason for exclusion),
- Randomised,

- Allocated to each randomisation group,
- That received each allocated intervention,
- That did not receive each allocated intervention,
- Lost to follow-up (and the frequency of each reason for loss to follow-up) for each randomisation group,
- Analysed for each randomisation group,
- Not analysed (and the frequency of each reason for not being analysed) for each randomisation group.

#### **10.3.2. Outcome Analysis**

Summary measures of all baseline variables will be calculated and reported. Primary and secondary outcomes will be compared between the two groups (Low AGE Diet vs. Standard Diet) at 6 months using a t-test if data are normally distributed or a Mann Whitney U test if not. Analysis will be by intention to treat.

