### **3.2. Outcome**

**Primary outcome:** SAF values at 6 months.

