**Secondary outcomes:**

- Participant adherence to dietary intervention (achieving dietary AGE intake <8000 kilounits [kU]/day).
- Slope of SAF values over 6 months.
- Change in SAF values at 6 months.
- Change in weight over 6 months.
- Change in aortic pulse wave velocity (aPWV).
- Change in high-sensitive C reactive protein (hsCRP).
- Change in quality of life.

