#### 7.4. Study Assessments

Once eligible participants have read the PIS and given their informed consent, relevant participant characteristics will be extracted either from electronic data captured in medical records and from a self-reported questionnaire at baseline and will include demographic characteristics, educational level, employment status, duration of renal replacement therapy, transplant type and vintage, number of rejection episodes, aetiology of CKD, medical history (e.g. history of cardiovascular disease, diabetes and hypertension), current co-morbidities, alcohol history, smoking status and current medication.

The accumulation of AGEs will be assessed by measuring SAF using a validated Autofluorescence Reader Standard Unit version 2.4.3 (AGE Reader, DiagnOptics, Groningen, The Netherlands) at baseline, 3 and 6 months, as described in more detail elsewhere (Shardlow et al., 2020). In brief, the AGE Reader directs an ultraviolet excitation light (intensity 300-420 nm) through an illumination window of approximately 1 cm^2 on a skin area (free of visible vessels, scars, tattoos or any other skin irregularities) of the volar surface of the forearm at approximately 10 cm below the elbow. The AGE Reader then measures the amount of emitted light that is reflected back from the skin (intensity 300-600 nm) using a spectrometer (AVS-USB2000, Avantes Inc., Eerbeek, The Netherlands) and a 200-µm glass fibre. SAF is calculated by dividing the average emitted light intensity in the range between 420-600 nm by the average excitation light intensity in the range between 300-420 nm and expressed as arbitrary units (AU). Three measurements will be obtained and the average of these will be used for analysis. Valid SAF readings cannot be obtained when the skin reflectivity is lower than 6% (Mulder et al., 2006); therefore, persons with dark skin colour (i.e. Fitzpatrick skin colour type V-VI), who have an ultraviolet reflectance of less than 6%, will be excluded from this study.

Routine blood/laboratory tests will be performed at baseline, 3 and 6 months and will include haemoglobin, white cell count, hsCRP, glucose, HbA1C, urea, creatinine, potassium, phosphate, calcium, sodium, albumin, total proteins, cholesterol, triglycerides, intact parathyroid hormone and immunosuppression levels.

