#### **10.5. Adjusted analyses**

As this is a feasibility study, we do not plan to conduct adjusted analyses.

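### The primary 6-month SAF comparison leaves out baseline SAF although it is measured; precision is lost to an extent set by a baseline to 6-month correlation that the documents do not give

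*Combined protocol and SAP*

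**What the plan says.** - **Primary outcome (3.2).** "SAF values at 6 months", that is, the raw value and not the change.
- **Test (10.3.2).** "Primary and secondary outcomes will be compared between the two groups (Low AGE Diet vs. Standard Diet) at 6 months using a t-test", or a Mann-Whitney U test if the data are not normal. The opening of section 10 repeats this: "Intergroup comparisons will be performed using Mann Whitney test or Student t test for continuous variables".
- **Adjustment (10.5).** "As this is a feasibility study, we do not plan to conduct adjusted analyses". No other reason is given.
- **Baseline measurement (7.4).** SAF is taken "at baseline, 3 and 6 months, as described in more detail elsewhere". Section 10.3.1 summarises baseline SAF by group, but nothing brings it into the primary comparison.
- **Secondary outcomes (3.2).** Two of them use baseline SAF: "Change in SAF values at 6 months" and "Slope of SAF values over 6 months".
- **Sample size (10.1).** No formal calculation is said to be needed. With a control-group value of 2.81 ± 0.64 AU, a difference of 0.6 AU and alpha 0.05, "having a sample size of 18 in each group would give 80% power". The target of 40 allows for 10% drop-out.
- **Objectives (3.1).** These include estimating the intervention's effects so that a larger trial can be sized.

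**The concern.** SAF varies widely between people. Any part of that variation that persists over six months sits in the error term of an unadjusted comparison, although the baseline value could remove it. With about 36 evaluable participants, the confidence interval for the effect will be wide in any case. That interval matters here because the effect estimate is meant to inform a larger trial. A model that includes baseline SAF targets the same mean difference in AU, so the question is one of precision: how much is given up, and whether the planned change score and slope already recover it.

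**Working it through.** **Inputs.** From 10.1: SD 0.64 AU, difference 0.6 AU, 18 per group, alpha 0.05 (two-sided reproduces the plan's figure; one-sided would give 15 per group). Assumed: r, varied from 0 to 0.7, and that 0.64 describes the enrolled sample.

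**1. The plan's own figure.** Normal approximation: n = 2 × [0.64 × (1.960 + 0.842)/0.6]² = 17.9, so 18 per group. Power at 18 is 80.3%, and 36/0.9 = 40. All of this reproduces. The steps below use the noncentral t distribution for both methods, so that they are compared on one basis. That is why the unadjusted figure there is 78.0%; the difference from 80.3% is not an error in the plan.

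**2. Unadjusted test.** SE = 0.64 × √(2/18) = 0.213 AU with 34 df. The 95% CI half-width is 2.032 × 0.213 = 0.434 AU, and power at 0.6 AU is 78.0%.

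**3. Linear model with baseline SAF.** Expected SE = 0.213 × √(1 − r²) × √(33/32) with 33 df. The factor 33/32 is the price of estimating the baseline slope when the arms differ by chance at baseline.

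**4. Change score.** With equal SDs at baseline and 6 months, SE = 0.213 × √[2(1 − r)] with 34 df.

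| r | Unadjusted: half-width / power | With baseline SAF: half-width / power | Change score: half-width / power |
|---|---|---|---|
| 0 | 0.434 / 78.0% | 0.441 / 76.7% | 0.613 / 48.9% |
| 0.3 | 0.434 / 78.0% | 0.420 / 80.5% | 0.513 / 63.7% |
| 0.5 | 0.434 / 78.0% | 0.382 / 87.4% | 0.434 / 78.0% |
| 0.7 | 0.434 / 78.0% | 0.315 / 96.4% | 0.336 / 94.1% |

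**5. Break-even.** The half-widths in steps 2 and 3 are equal when (1 − r²) × (33/32) × (2.0345/2.0322)² = 1, which gives r = 0.180. These are expectations. In 40,000 simulated trials per r, the adjusted interval was the narrower one in 21% at r=0, 44% at r=0.2, 66% at r=0.3, 94% at r=0.5 and over 99% at r=0.7.

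**6. When the change score beats the raw value.** Var(change) = s₀² + s₆² − 2r·s₀·s₆, where s₀ and s₆ are the SDs at baseline and 6 months. This is below s₆² only if r > 0.5 × s₀/s₆. With equal SDs the threshold is 0.5.

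**7. The slope.** With complete visits at 0, 3 and 6 months, as in 7.4, the least-squares slope is Σ(t − 3)y / Σ(t − 3)² = (3y₆ − 3y₀)/18 = (y₆ − y₀)/6. This is the change score divided by 6, so the 3-month value drops out and the slope has the same power as the change score.

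**8. Selection on SAF.** Section 6.1 admits only people whose SAF exceeds the general-population mean for age. If 0.64 is the SD before that selection, both the SD and r fall in the enrolled sample. I simulated three equally correlated normal measurements (screening, baseline, 6 months) and kept people above a single cut on the screening value:

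| Cut | r before | r after | SD after | Power: unadjusted to adjusted |
|---|---|---|---|---|
| Recipients' mean | 0.5 | 0.41 | 0.59 | 85% to 89% |
| Recipients' mean | 0.7 | 0.56 | 0.53 | 91% to 97–98% |
| 1 SD below the mean | 0.5 | 0.45 | 0.61 | 82% to 88% |
| 1 SD below the mean | 0.7 | 0.63 | 0.58 | 86% to 97% |

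The gain shrinks to about 5 to 7 points with the cut at the mean, and to about 7 to 12 points with the lower cut. The real cut is probably nearer the milder one, because the assumed recipient mean of 2.81 exceeds every age-group mean in Appendix 1 (highest 2.73).

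**The case against.** The strongest reply is that this is a declared choice. Section 10.5 says openly that there will be no adjusted analyses, 10.1 disclaims a formal sample size, the test is valid, and two secondary outcomes already use baseline SAF. The size of the loss rests on an r that nobody has stated, and at r of 0.3 or less there is little to gain. The SD, r and residual SD could also be computed from the collected data whatever the primary test is, so planning of the larger trial is not blocked.

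Much of this stands. The size is conditional, 0.18 marks break-even rather than a material loss, and later planning is limited rather than prevented. Two parts do not stand. Feasibility is not in itself a reason against one pre-specified covariate when 3.1 asks for effect estimates. And the change score and slope are less precise than the adjusted estimate at each r tabulated above; at r=0.3 they are clearly worse than the raw value (64% against 78%).

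A reader might infer that the planned comparison is biased or that the sample size is wrong. The documents support neither: randomisation protects the unadjusted test, and 18 per group reproduces.

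A reader might also infer that a worthwhile loss is certain. Appendix 1 makes some correlation plausible: equal numbers in the five age bands from 30 to 80 would give a between-band variance of about 0.145, against 0.64² = 0.410. But that assumes an age mix and carries reference-population means over to selected recipients. It does not establish r.

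**Conclusion.** The point holds as one of lost precision only. If 0.64 AU and r describe the enrolled sample of 18 per arm, adjusting for baseline SAF changes power at 0.6 AU from 78% to 77% (r=0), 80% (r=0.3), 87% (r=0.5) or 96% (r=0.7), and the expected CI half-width from 0.43 AU to 0.44, 0.42, 0.38 or 0.31 AU. The trade is lopsided: at worst about one power point is lost, and at r of 0.5 or more the gain is about 9 points or more. If 0.64 is the SD before selection on SAF, the gain is smaller. The statement that the change score needs r above 0.5 rests on equal baseline and 6-month SDs, and the slope identity rests on complete visits at the times in 7.4.

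**What to change.** - **10.3.2.** Make the primary estimate a pre-specified linear model of 6-month SAF on arm and baseline SAF. Report the adjusted mean difference in AU with its ordinary model-based 95% CI, the residual SD, and r with its CI. Keep the unadjusted test as a sensitivity analysis.
- **10.5 and the intergroup-test sentence at the start of section 10.** Edit both to match.
- **Skewed residuals.** Keep the ordinary model interval and do not add a bootstrap fallback. In simulations with skewed residuals at 18 per arm, a percentile bootstrap covered about 92% to 93%, against about 95% to 96% for the model interval.
- **Use of r in planning.** Quote it only with its interval. An observed r of 0.5 from 36 people has a 95% CI of about 0.21 to 0.71 (Fisher z), so the variance factor 1 − r² could lie anywhere from about 0.96 to 0.49.

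**Cost.** Wording in three places, with no new data and no new software. The model uses one degree of freedom, at worst about one power point (78.0% to 76.7% at r=0).

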## **3. OBJECTIVES AND OUTCOME MEASURES/ ENDPOINTS**

### **3.1. Objectives**

The aim of this study is to establish the feasibility of conducting a definitive RCT which will investigate whether a low AGE diet leads to reduced SAF levels and improves cardiovascular health in kidney transplant recipients.

This innovative proposal is designed to test the feasibility of answering the question:

Does a low AGE diet reduce SAF levels and improve cardiovascular health in kidney transplant recipients?

Specifically, this study will address:

- Whether it is possible to conduct an RCT of the dietary intervention compared to a standard diet for kidney transplant recipients.
- Whether the intervention is acceptable, and participant views and experiences of the intervention.

Specifically, this study will address the following:

- Eligibility, recruitment and dropout rates, with reasons for loss to follow-up.
- Proportion of eligible participants recruited.
- The suitability and sensitivity of outcome measures for use in a larger trial.
- The most appropriate primary outcome measure for use in a larger trial and completeness of data.
- Estimates of the effects of the intervention to inform a sample size calculation for a larger trial.
- The feasibility of health economic data collection and preliminary cost data collection and calculations.

- The feasibility of delivering the intervention to the population group.
- Fidelity and adherence with the intervention.
- Determine whether the intervention is acceptable and participant views and experiences of the intervention.

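### Effect estimates are a stated objective, but the analysis names only hypothesis tests, switches the primary comparison on an undefined normality criterion, and rules out adjustment for baseline SAF

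*Combined protocol and SAP*

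**What the plan says.** All references are to the combined protocol and SAP.

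- **Objective.** Section 3.1 lists among its specific aims "Estimates of the effects of the intervention to inform a sample size calculation for a larger trial".
- **Primary outcome.** Section 3.2 gives "SAF values at 6 months", a continuous measure in arbitrary units (AU).
- **General methods.** Section 10 states "Intergroup comparisons will be performed using Mann Whitney test or Student t test for continuous variables", with no rule for choosing between the two.
- **Outcome analysis.** Section 10.3.2 compares primary and secondary outcomes between arms at 6 months "using a t-test if data are normally distributed or a Mann Whitney U test if not". The only summaries that section promises concern baseline: "Summary measures of all baseline variables will be calculated and reported".
- **Normality check.** Section 10.3.1 names one, "if shown to be normally distributed, using a combined skewness and kurtosis test", but only to decide how baseline variables are described. None is named for outcomes.
- **Adjustment.** Section 10.5 says "we do not plan to conduct adjusted analyses", on the ground that this is a feasibility study.
- **Data available.** Section 7.4 measures SAF at baseline, 3 and 6 months.

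**The concern.** To size a definitive trial on SAF, its designers need a between-group difference in AU, the uncertainty around it, and an SD. The plan's own calculation in section 10.1 uses exactly such inputs (0.6 AU and 0.64 AU). The outcome analysis commits to none of them.

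The switch adds to the gap. A t-test compares means. A Mann-Whitney test compares ranks, and unless the two distributions differ only by a shift it does not address the same quantity. Its result is a rank statistic and a p-value, with no difference in AU and no SD. Which of the two is produced depends on a check with no stated method, threshold or target (pooled values, each arm, or residuals). Two analysts following the text could reach different primary analyses from the same data.

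Finally, when the aim is an estimate from about 36 people, leaving out a baseline measurement of the outcome itself gives up precision that costs nothing to obtain.

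**Working it through.** **Inputs from the plan (sections 10.1 and 10.8).** SD 0.64 AU; difference 0.6 AU; alpha 0.05, taken as two-sided; 18 per arm; 40 recruited; 10% drop-out; missing data omitted, so about 18 per arm analysed.

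**Step 1: reproduce the plan's figure.** n per arm = 2 × (1.960 + 0.842)² × 0.64² / 0.6² = 17.9, rounded up to 18. Normal-approximation power at 18 per arm is 80.3%, and 36 / 0.9 = 40. Section 10.1 reproduces and is not challenged. (A one-sided alpha would give 15, so two-sided is the reading that fits.)

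**Step 2: what an estimate would look like.** Unadjusted 95% CI half-width = t(34) × SD × √(2/n) = 2.032 × 0.64 × √(2/18) = 0.43 AU. An observed difference of 0.6 AU would have a CI of about 0.17 to 1.03 AU.

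The pooled SD has a 95% CI of 0.64 × √(34/χ²), using the 97.5% and 2.5% points of χ² on 34 df: about 0.52 to 0.84 AU. To show why this matters, suppose the larger trial targets 0.3 AU at 90% power (both assumed; the documents give neither). Then n per arm = 2 × (1.960 + 1.282)² × SD² / 0.3², which is 96 at SD 0.64 and 165 at SD 0.84.

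**Step 3: adjusting for baseline SAF.** Half-width = t(33) × 0.64 × √(1 − r²) × √(2/18), with t(33) = 2.035 and r the baseline-to-6-month correlation. The documents give no r, so a range is shown.

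| Assumed r | Adjusted half-width (AU) |
|---|---|
| 0.5 | 0.38 |
| 0.6 | 0.35 |
| 0.8 | 0.26 |
| 0.9 | 0.19 |

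The formula takes the arms as balanced on baseline SAF; chance imbalance would widen these slightly.

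**Step 4: how the switching rule behaves.** It was simulated with 20,000 trials per scenario, 18 per arm and SD 0.64. Because the plan defines no outcome check, a skewness-kurtosis test at 0.05 was assumed, applied either to pooled values or to each arm.

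| Data | Share switched to Mann-Whitney (difference 0 or 0.6 AU) | Power at 0.6 AU: rule | Power at 0.6 AU: always t-test |
|---|---|---|---|
| Normal | 5–11% | 78.2–78.4% | 78.4% |
| Mild skew (lognormal) | 17–28% | 78.4–79.4% | 77.8% |
| Clear skew (gamma, shape 2) | 42–64% | 83.6–85.2% | 78.6% |

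Type I error of the rule was about 4.7% to 5.7% across scenarios. Switching is thus a realistic event, but it does not damage error rates here.

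**The case against.** **The estimate can still be recovered.** A t-test is built from the mean difference and its standard error, and arm means and SDs can be calculated whichever test is used. Section 3.1 itself commits the study to estimates, and nothing restricts reporting to p-values. This stands to the extent that the fault is an estimate not specified, rather than one that cannot be had. A reader might infer that the objective will not be delivered, or that the larger trial will be sized from a p-value; the documents say neither. The objective nonetheless has no matching analysis, and the choice of summary is left until the data are seen.

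**The switch does no harm to operating characteristics.** This stands. A reader might infer a power loss because Mann-Whitney is slightly less powerful than the t-test on normal data. Section 10.3.2 uses it only when data are judged non-normal, and the rule as simulated lost essentially no power with normal data and gained some with skewed data.

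**The skewness-kurtosis test belongs to baseline description.** This also stands. A reader might carry it over from section 10.3.1 and criticise its weakness at 18 per arm. The text does not apply it to outcomes; the sound criticism is that the outcome criterion is undefined.

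**Section 10.5 declines adjustment deliberately, and section 3.2 already lists change in SAF and its slope.** The choice is explicit, and the adjusted half-widths depend on an unknown correlation. But feasibility status is no reason to give up precision when one of the objectives is itself an effect estimate. Change in SAF is a secondary outcome and a less efficient use of baseline. With equal SDs at both visits its half-width is 2.032 × 0.64 × √(2(1 − r)) × √(2/18), which is 0.43, 0.39, 0.27 and 0.19 AU at r = 0.5, 0.6, 0.8 and 0.9. Covariate adjustment does as well or better at each of these.

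**Conclusion.** The point holds as a gap between objective and analysis. Effect estimates are promised, but only tests are specified; the primary quantity can change with an undefined normality judgement; and baseline SAF goes unused in the primary comparison. The consequence is a data-dependent estimand, an unspecified estimate and lost precision. It does not extend to the sample size, the type I error or the power of the switching rule.

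The unadjusted half-width of 0.43 AU compares with a design difference of 0.6 AU. Adjustment would reduce it to somewhere between 0.38 and 0.19 AU over correlations of 0.5 to 0.9. These figures assume that the plan's SD of 0.64 AU applies at 6 months and that 18 per arm are analysed. The SD among participants selected for SAF above the age mean (section 6.1) may differ, which is a further reason to report it.

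This should be corrected before analysis. Data collection is not affected.

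**What to change.** - **Section 10.3.2:** pre-specify one linear model for 6-month SAF, with treatment group and baseline SAF as terms, used whatever the normality result. Report the mean difference in AU with its 95% CI, the SD of 6-month SAF by arm, and the baseline-to-6-month correlation. Keep Mann-Whitney as a sensitivity analysis only, and drop normality as a decision rule for the primary comparison.
- **Section 10.5:** amend it, since this model reverses the present exclusion of adjusted analyses. One sentence allowing adjustment for baseline SAF is enough.
- **Section 10:** align the general list of tests with the new wording.

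If the sponsor prefers to leave section 10.5 as it is, the minimum is to commit to the unadjusted mean difference, its 95% CI and the SD by arm regardless of distribution. That closes the gap with section 3.1 but forgoes the gain in precision.

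The cost is a change of wording. Baseline and 6-month SAF are already collected, and no extra visits, measurements or participants are needed.
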